5. Use of SREC e-cigarette: The side effects of SREC may be similar to other commercially available vaping devices. Such devices can expose users to several chemicals, including nicotine, carbonyl compounds, and volatile organic compounds, known to have adverse health effects. The health effects and potentially harmful doses of heated and aerosolized constituents of e-liquids, including solvents, flavorants, and toxicants, are not completely understood. E-cigarette aerosol is not harmless "water vapor" although it generally contains fewer toxicants than combustible tobacco products. Specific potential known risks include:
 - a. Refill pods that will be used in this study contain nicotine. Nicotine is an addictive chemical. It is possible that this experience could lead to long-term use of e-cigarettes after the trial is over.
 - b. Nicotine may contribute to some of the disease associated with smoking
 - c. The most common side effects related to e-cigarette use are changes in taste, mucus in throat/sinus, dry mouth, dry cough, throat irritation, sore

throat, mouth ulcers, dizziness, headache, and nausea, difficulty breathing, heart palpitations, vomiting, abnormal heart rate, stomach discomfort, rash, chest pain.

- d. Although uncommon, batteries from e-cigarettes have exploded/ignited and injured users.
- e. E-cigarettes can overheat and present a minor burn risk if the button is turned on repeatedly.
- f. Ingestion of e-liquids containing nicotine can cause acute toxicity and possible death if e-liquids containing nicotine are consumed. Participants will be directed to keep device and all e-liquid refill cartridges away from pets and children.
- g. On rare occasions, allergic reactions have occurred after using e-cigarettes.
- h. Severe lung disease has been associated with using e-cigarette/vaping products. The CDC and FDA continue to investigate, but the majority of cases have involved the use of cannabis oil, such as THC, obtained on the black market. In addition, one of the chemicals of concern is the addition of Vitamin E acetate to e-liquid cartridges and pods.

6. Dual Use of Tobacco or Nicotine Products: There is also the chance of use of more than one product (e.g., continued smoking among participants) and/or continued use of the products. Cessation of all tobacco products will be strongly recommended to the subjects both at the end of the experimental phase and at follow-up.

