7. Smoking Withdrawal: Participants may experience smoking withdrawal symptoms during this study. The symptoms can be uncomfortable but are typically of minimal risk. Smoking withdrawal symptoms include:

- a. Anger, irritability, frustration
- b. Anxiousness, nervousness
- c. Depressed mood or sadness
- d. Desire or craving to smoke
- e. Difficulty concentrating
- f. Increased appetite, hunger or weight gain
- g. Insomnia, problems sleeping or awakening at night
- h. Restlessness
- i. Impatience
- j. Constipation
- k. Dizziness
- l. Coughing
- m. Dreaming or nightmares
- n. Nausea
- o. Sore Throat

8. Returning to Regular Smoking: It is possible that if participants return to smoking their usual brand of cigarette at the end of the study they may experience mild and transient nausea, dizziness, and lightheadedness.

9. Changes in Blood Pressure and/or Heart Rate: Smoking and nicotine can affect the cardiovascular system which may result in changes in blood pressure and/or heart rate.
10. Changes in Mood, Emotions and Psychiatric Symptoms: Smoking and nicotine can affect a person's mood and emotions and are associated with psychiatric disorders including major depressive disorder, general anxiety disorder, bipolar disorder and eating disorders. Any changes in nicotine use or cigarette consumption could adversely affect mood, emotions and the symptoms related to psychiatric conditions in some individuals.
11. Risk to Fetus: Smoking during pregnancy can lead to miscarriage, preterm delivery, stillbirth, low birth weight, problems with the placenta, birth defects such as cleft palate, sudden infant death syndrome (SIDS), early childhood behavioral problems, altered lung development and possible propensity for addiction. Although unknown, similar effects could occur with the use of vaping devices.
12. Smoking and Oral Contraceptives in Women: Women who smoke and are over the age of 35 should not take oral contraceptives that contain estrogen without consulting their physician. Smoking while using oral contraceptives can increase the risk of having a cardiovascular event such as a heart attack or stroke. Additionally, there is a potential risk of thrombosis associated with hormonal therapy (including contraceptives) and smoking.

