 - The 'Adverse Event Log' and 'Blood Pressure and Heart Rate Symptom Checklist' will be completed if an automatic and subsequent manual blood pressure measurement during the same visit is below 90 systolic or 50 diastolic and the participant is experiencing symptoms listed on the 'Blood Pressure and Heart Rate Symptom Checklist.'
- **Heart Rate:**
 - The 'Adverse Event Log' and 'Blood Pressure and Heart Rate Symptom Checklist' will be completed if an automatic and subsequent manual heart rate measurement during the same visit is at or above 105 bpm.
 - The 'Adverse Event Log' and 'Blood Pressure and Heart Rate Symptom Checklist' will be completed if an automatic and subsequent manual heart rate measurement during the same visit is below 45 bpm and the participant is experiencing symptoms listed on the 'Blood Pressure and Heart Rate Symptom Checklist.'

Adverse Events Communicated by Participants

The occurrence of AEs will be sought by non-directive questioning of the participant at each visit during the study. AEs also may be detected when the participant volunteers them during or between visits or through physical examination, laboratory test, or other assessments.

Review and Reporting of Adverse Events and Serious Adverse Events

Co-Principal Investigators with oversight from [name]. (Medical Monitor) and [name] (Nurse Practitioner) will review all AEs and assess whether they are related to the study product.

PROTOCOL TITLE: Biomarkers in SREC Users

VERSION DATE: 03/13/2024

An AE is defined as the appearance or worsening of any undesirable sign, symptom, or medical condition occurring after starting the study procedures even if the event is not considered to be related to the study product. Medical conditions/diseases present before starting the study are only considered adverse events if they worsen after starting the study product. Abnormal laboratory values or test results constitute adverse events only if they induce clinical signs or symptoms, are considered clinically significant, or require therapy; there are no plans for active monitoring of laboratory tests as part of this project. Withdrawal symptoms are considered adverse event if the symptom had a significant impact on the participant's daily life, caused a major disruption of functioning, or took any medication for it.

To the extent possible, each adverse event will be evaluated to determine:

1. the severity grade (mild, moderate, severe)

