2. its relationship to the study product used (suspected/not suspected)
3. its duration (start and end dates or if continuing at final exam)
4. outcome (resolved/improved/unchanged/worsened; study product temporarily interrupted or permanently discontinued due to this adverse event; concomitant medication taken; non-drug therapy administered)
5. whether it constitutes a SAE

Information about all SAEs will be collected and recorded on the project's Serious Adverse Event Report Form. A SAE is defined an undesirable sign, symptom or medical condition which:

1. is fatal or life-threatening;
2. requires or prolongs hospitalization;
3. results in persistent or significant disability/incapacity;
4. constitutes a congenital anomaly or a birth defect;
5. is medically significant, in that it may jeopardize the subject and may require medical or surgical intervention to prevent one of the outcomes listed above.

Events not considered to be SAEs are hospitalizations that are:

1. elective or pre-planned, for a pre-existing condition that is unrelated to the products under study and did not worsen;
2. for general care, and/or overnight observation;
3. treatment on an emergency, outpatient basis for an event not fulfilling any of the definitions of serious given above and not resulting in hospital admission.

Safety evaluation will be performed on all accrued participants for whom SREC was dispensed. The assessment of safety will be based on the frequency of AEs and severity grade of AEs. Other safety data (e.g. CO, vital signs) will be considered as appropriate.

SAEs occurring after the participant has signed the consent form and until 4 weeks after the participant has stopped use of study product that are unexpected and at least possibly related will be reported. SAEs occurring more than 4 weeks after study discontinuation need only be reported if a relationship to study product is suspected. All AEs will be summarized by presenting, for each treatment group, the number and percentage of participants who experienced any AE, the number reporting AEs in each body system and

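### Mild dizziness, cough, nausea or sore throat can be labelled withdrawal and left out of the AE count, because section 17.2 sets an impact threshold for withdrawal symptoms and no rule for telling them from SREC effects

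*Combined protocol and SAP*

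**What the plan says.** Section 17.2 (Data Safety Monitoring) starts from a wide definition: "An AE is defined as the appearance or worsening of any undesirable sign, symptom, or medical condition occurring after starting the study procedures". It adds that an event counts even when it is thought unrelated to the product, and it sets no minimum severity.

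Later in the same paragraph comes an exception: "Withdrawal symptoms are considered adverse event if the symptom had a significant impact on the participant's daily life", or the symptom "caused a major disruption of functioning, or took any medication for it". A withdrawal symptom that meets none of these three conditions is not an AE.

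Section 13.1 (Foreseeable Risks) contains two lists that bear on this.

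- Item 5, on use of SREC, says: "The side effects of SREC may be similar to other commercially available vaping devices". Its sub-item c begins "The most common side effects related to e-cigarette use are changes in taste, mucus in throat/sinus, dry mouth, dry cough, throat irritation" and continues, after a page break that falls inside the term sore throat, with "throat, mouth ulcers, dizziness, headache, and nausea, difficulty breathing" and further terms.
- Item 7, on smoking withdrawal, opens with "Participants may experience smoking withdrawal symptoms during this study" and lists 15 lettered entries, including dizziness, coughing, nausea and sore throat.

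On evaluation, section 17.2 states: "The assessment of safety will be based on the frequency of AEs and severity grade of AEs". Section 15.1 says that AEs and SAEs will be tabulated.

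**The concern.** The general definition leaves cause out of the decision to record. Cause is judged afterwards, through the relationship field (suspected or not suspected) and the review of all AEs by the investigators with medical oversight. The exception reverses that order for withdrawal symptoms: someone must first decide that a symptom is withdrawal, and if it falls below the threshold it never reaches the relationship field or the review.

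That is harmless for symptoms that only withdrawal would explain, such as craving or increased appetite. It matters where the protocol names the same symptom as an expected effect of vaping. Every participant starts SREC and is asked to stop smoking a few days later, so both explanations are open for most of the study. The study is meant to yield reference data on SREC, and its safety summary rests on AE frequency and grade. If part of the mild end of the product's own expected profile can be filed elsewhere, the table may show SREC as better tolerated than it was.

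**Working it through.** The plan states no figure on this point, so the check is a comparison of texts, followed by a short illustration of scale.

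**1. Match the two lists in section 13.1.** Item 5c has 17 terms: changes in taste, mucus, dry mouth, dry cough, throat irritation, sore throat, mouth ulcers, dizziness, headache, nausea, difficulty breathing, palpitations, vomiting, abnormal heart rate, stomach discomfort, rash and chest pain. Item 7 has 15 entries (a to o).

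| Item 5c (e-cigarette effect) | Item 7 (withdrawal) | Match |
|---|---|---|
| Dizziness | Dizziness (k) | identical |
| Nausea | Nausea (n) | identical |
| Sore throat | Sore throat (o) | identical |
| Dry cough | Coughing (l) | near match |

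The overlap is 3 + 1 = 4 of 17 side effects (24%).

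**2. Follow one event through section 17.2.** Take a new, mild, unmedicated cough after the quit date.

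- Judged a product effect, or of unknown cause: an AE under the general definition, then graded, assessed for relationship and reviewed.
- Judged withdrawal: below all three triggers, so not an AE. No relationship entry or review is required.

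The outcome turns on a label for which no section gives a criterion.

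**3. Look for another route into the AE count.**

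- Health Changes Questionnaire: a positive answer leads the interviewer to assess for an AE, which returns to the same definition.
- Respiratory questionnaire: the item that prompts the AE log (question 6) asks about illness such as a cold or flu. A cough or sore throat without illness need not trigger it.
- Adverse Events Scale (section 3.4): concerns events tied to use of tobacco products, so it too depends on attribution.
- Table 3 lists no withdrawal scale that would hold the symptoms falling below the threshold.

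**4. Direction.** Labelling a product effect as withdrawal removes an AE. The opposite error adds nothing improper, because the general definition counts symptoms whatever their cause, and the relationship field can then show the doubt. Measured against that definition, error runs one way only.

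**5. Scale, by assumption only.** Let p be the share of participants with one such symptom, and s the share of those symptoms that are both below the threshold and labelled withdrawal. Neither is in the documents. Take n = 30, the completer goal; the safety set is everyone given SREC and may be larger. The expected recorded count is 30 × p × (1 − s), and the chance of recording at least one is 1 − (1 − p(1 − s))^30.

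| p | s = 0 | s = 0.5 | s = 1 |
|---|---|---|---|
| 5% | 1.5 (0.785) | 0.75 (0.532) | 0 (0) |
| 10% | 3.0 (0.958) | 1.5 (0.785) | 0 (0) |
| 20% | 6.0 (0.999) | 3.0 (0.958) | 0 (0) |

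The result runs from no loss to complete loss according to s alone, so this shows the mechanism and does not estimate the undercount.

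**The case against.** A threshold for expected withdrawal symptoms is a sensible choice in a switching study, and without one the AE log could fill with cravings and irritability. The lists in section 13.1 are risk disclosure, section 17.2 does not refer to them, and nothing obliges staff to label every item 7 symptom as withdrawal. AEs are only tabulated; no hypothesis depends on these four terms, and the SAE criteria are separate. The Adverse Events Scale and the respiratory questionnaire are given from Baseline 2 onward, and nothing says that the exception filters them. All of this stands. It makes the loss conditional and leaves open how much of the information survives elsewhere. It does not supply an attribution rule or a sure route into the AE count.

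A reader might also infer more than the text supports:

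- **That only disabling symptoms count.** A significant effect on daily life is enough, and so is any medication.
- **That moderate events are lost too.** The grades are not defined, and a moderate symptom may well meet a trigger. Only mild, unmedicated events are clearly exposed.
- **That staff cannot tell the causes apart.** Section 5.2 sets the quit date about 3 to 5 days after product assignment and encourages SREC use in between. Onset in that window points towards the product, though some participants may already be smoking less. What is missing is a rule, especially after the quit date.
- **That the undercount is some definite multiple.** Any such figure merely restates an assumed attribution share.
- **That the protocol ascribes these symptoms to SREC.** It ascribes them to e-cigarettes generally and says that SREC may be similar.

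**Conclusion.** The concern holds in a limited form. Mild, unmedicated dizziness, cough, nausea and sore throat can be left out of the AE count on an unguided judgement that they are withdrawal, made before any relatedness assessment and with no comparison arm to expose the error. The size that the documents support is the overlap: 4 of the 17 listed side effects. The direction, relative to the plan's general AE definition, is downward; the amount is unknown and could be close to nil if staff seldom use the withdrawal label. The conclusion assumes that the exception in section 17.2 governs what is tabulated as an AE, which is its plain reading. The item content of the questionnaires is not in the documents, so total loss of the information is not shown. It is worth correcting because the change is small and unrecorded mild events may not be recoverable later.

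**What to change.** Amend the exception in section 17.2 so that the impact threshold applies only to symptoms found solely on the withdrawal list. For dizziness, cough, nausea and sore throat, record an AE at any grade when the symptom is new or worse than at Baseline 2, using the severity, start-date and relationship fields already planned. Tabulate these four separately as 'possible product or withdrawal effect', so that AE totals can be shown with and without them. State the date from which the rule applies, since participants seen before it will have been recorded under the present wording.

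The cost is a sentence or two in section 17.2, some extra mild entries in the AE log and a slightly less favourable AE table. No visit or instrument is added, although staff should make sure that the presence of the four symptoms is noted at Baseline 2 if the existing forms do not already ask. The change concerns recording and reporting only.

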12.0 Withdrawal of Participants

12.1 Withdrawal Circumstances

If a participant is unable to achieve cessation (confirmed biologically either via CO or urine) within the first two weeks of the study, the participant will be withdrawn. Additionally, a study participant may be discontinued from the study if investigators determine that this is the best decision in order to protect his/her safety. If a participant either withdraws from the study or the investigators decide to discontinue a participant due to an adverse event (AE) or serious adverse event (SAE), the participant will have appropriate follow-up assessments and if necessary, referrals will be made for medical care. The participant experiencing an AE/SAE will be followed until the problem resolves, stabilizes, or is clearly unrelated to the study product. Any AE that remains open will be reviewed and closed at the Week 10 follow-up interview.

For the participant's protection, they will be withdrawn immediately from the study if any of the following occur:

- 1) Cardiovascular disease (CVD) event: Typically includes MI (heart attack), PTCA (angioplasty/stenting), bypass surgery, stroke, or peripheral vascular disease. Less common CVD problems would be new cardiac arrhythmias (e.g., new atrial fibrillation) or new valvular disease (e.g., mitral or aortic regurgitation).
- 2) DVT/PE (deep vein thrombosis/pulmonary embolism, i.e., blood clots in the venous system).
- 3) Suicide Attempt: A participant will be withdrawn if he/she attempts suicide at any time during participation in the study.
- 4) Psychiatric Hospitalization: A participant will be withdrawn if he/she is hospitalized for psychiatric reasons at any time during participation in the study.
- 5) Pregnancy: If a participant becomes pregnant, she will be immediately withdrawn from the study. In addition, the licensed medical professional will follow-up after delivery to ask questions about the health of the baby.
- 6) Expired breath carbon monoxide increase: A participant will be withdrawn from the study if the average of the 2 (or 3) CO readings is 100 ppm or greater.

- 7) **Respiratory Illness Event:** A participant will be withdrawn if they develop a severe (hospitalized or the symptom had a significant impact on his/her activities) respiratory illness that is related or possibly related to the SREC product as determined by the licensed medical professional.

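### Section 17.2 takes overnight-observation admissions out of the SAE definition with no condition on cause or seriousness, and its two SAE reporting sentences run on different clocks

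*Combined protocol and SAP*

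**What the plan says.** Section 17.2 gives five criteria for an SAE. The second is that the event "requires or prolongs hospitalization", with no minimum length of stay. The fifth covers medically important events that could put the participant at risk and need intervention to avert one of the other serious outcomes.

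A list of exceptions follows, introduced by "Events not considered to be SAEs are hospitalizations that are". It has three entries:

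- The first entry reads "elective or pre-planned, for a pre-existing condition that is unrelated to the products under study and did not worsen", so it is limited both by cause and by course.
- The second entry reads, in full, "for general care, and/or overnight observation", with nothing to limit it.
- The third entry concerns emergency outpatient treatment, and only where this was "for an event not fulfilling any of the definitions of serious given above and not resulting in hospital admission".

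On reporting, the section says that SAEs between consent and 4 weeks after the participant ceases product use "that are unexpected and at least possibly related will be reported". For later events, "SAEs occurring more than 4 weeks after study discontinuation need only be reported if a relationship to study product is suspected".

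Section 13.1, item 5c, names chest pain, heart palpitations and difficulty breathing among the side effects of e-cigarettes. Section 15.1 has AEs and SAEs tabulated as the safety endpoints.

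**The concern.** The second exception is the only one of the three with no limit on why the participant was admitted. Taken at face value it cancels criterion 2 for any overnight observation stay, including one prompted by a symptom that the protocol itself associates with the product. Whether such an admission is called an SAE would then depend on how site staff resolve two statements in the same section. In a small single-arm study, one or two such decisions could be all the information there is on serious harm.

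The reporting sentences raise a second question. The first measures its 4 weeks from the end of product use and the second from study discontinuation, a term that Section 17.2 does not define. If the two starting points differ, there can be a stretch of time that neither sentence covers.

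**Working it through.** The documents give no SAE rate or safety threshold, so there is no stated figure to reproduce. The check is a reading of the text plus one date calculation.

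**Step 1: the exceptions side by side (Section 17.2).**

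| Exception | Condition on cause | Condition on seriousness |
|---|---|---|
| 1. Elective or pre-planned | Pre-existing condition, unrelated to the products | Condition did not worsen |
| 2. General care or overnight observation | None | None |
| 3. Emergency outpatient treatment | None | Meets no serious definition, no admission |

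**Step 2: a test case.** A participant using SREC develops new chest pain and is kept in hospital overnight for observation.
- Criterion 2 is met, because the event required hospitalization.
- Exception 2 also applies, because the stay was for overnight observation.
- The lead-in says that events of the listed kinds are not SAEs. Read literally, the exception wins.
- If the exceptions are read as qualifying criterion 2 only, the event could still be an SAE under criterion 5, or under criterion 1 or 3 where those apply. The text does not say which reading is meant.

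**Step 3: what happens to the event if it is not an SAE.** It remains an AE. The Health Changes Questionnaire asks about medical care since the last visit, and Section 17.2 has all AEs summarized by number, body system and type. The attributes it lists for each AE are severity, relationship, duration, outcome and SAE status. None of these names hospital admission, although the Adverse Events Scale in Section 3.4 includes action taken, which might capture it. The event is therefore kept, but its label, and possibly the fact of admission, may be lost.

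**Step 4: the two clocks.** Let *s* be the week product use stops and *d* the week of study discontinuation. The first window closes at *s* + 4 and the later rule opens after *d* + 4, so the uncovered interval is (*d* + 4) − (*s* + 4) = *d* − *s*.
- Completer, with discontinuation read as the end of participation: *s* = 6 and *d* = 10 (Study Summary; Table 3). The first window closes at 6 + 4 = week 10 and the later rule opens after 10 + 4 = week 14. The uncovered interval is 4 weeks, from week 10 to week 14.
- Completer, with discontinuation read as stopping product: *s* = *d* = 6. Both fall at week 10 and the gap is 0.

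The protocol supports either reading. Section 5.3 counts the 4 follow-up weeks as participation, while Section 5.2 places the follow-up visit 4 weeks after the end of the study, which puts that end at week 6.

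**Step 5: the reporting conditions.** The first window needs two things together, unexpectedness and possible relatedness. The later rule needs only suspected relatedness. Section 17.2 does not define unexpectedness and names no reference for it.

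**The case against.** The strongest reply is that little is lost in practice. Criterion 5 can still make an observed cardiac or respiratory event serious. Every AE is tabulated, and Section 17.2 bases the safety assessment on the frequency and severity grade of AEs. All SAEs, expected or not, go on the SAE form. The planned summary covers SAEs and AEs with a suspected link to the product, and the investigators and the NIDA Scientific Officer review the reports. Investigators also review AEs at least monthly. The clock gap depends on one reading of a phrase, and the last scheduled contact is week 10.

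Most of this stands, and it rules out several stronger readings that a reader might draw:

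- **That these events would go uncounted or unreported.** They would not. At most they lose the SAE label, or fall outside one reporting sentence.
- **That harms listed in Section 13.1 would be treated as expected and so not reported during exposure.** No document makes Section 13.1 the reference for expectedness. Whether to keep an expectedness test at all is a matter of reporting policy, not an error.
- **That Section 12.1, item 7, contradicts the exception.** It says "A participant will be withdrawn if they develop a severe (hospitalized or the symptom had a significant impact on his/her activities) respiratory illness" when the illness is at least possibly related to SREC. That is a withdrawal rule with its own relatedness test and does not define a serious event. It does not follow that every admission meeting a withdrawal criterion is an SAE.
- **That one reclassified admission can be expressed as a rate among the 30 intended completers.** The safety evaluation covers everyone to whom SREC was dispensed, and that number is not given.

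What the reply does not remove is the conflict between criterion 2 and exception 2. The SAE form and the SAE table both depend on the classification, so neither can correct it. Nor does the week 10 visit settle the clock question, since the later rule is written for events that come to light after scheduled contact has ended.

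**Conclusion.** The point holds as a wording defect that can misclassify events. Followed literally, Section 17.2 can withhold SAE status from an overnight admission for a new and possibly product-related symptom, unless another seriousness criterion is held to prevail. Such an event would still be recorded and summarized as an AE. No rate can be attached, because the documents give neither an admission rate nor the number dispensed SREC.

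The clock mismatch is conditional. It leaves weeks 10 to 14 uncovered for a completer who stops product at week 6, if study discontinuation means the end of participation at week 10, and leaves no gap if it means stopping product. The different expectedness conditions are a point for explanation.

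The biomarker endpoints, their analysis and the power calculation are unaffected. The change is worth making because it costs almost nothing and concerns the SAE count that the study will present.

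**What to change.** In Section 17.2:

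1. Limit exception 2 to admissions that are unrelated to the study product, involve no new or worsened sign, symptom or condition, and meet no other seriousness criterion. This brings it into line with exceptions 1 and 3 and settles its relation to criteria 2 and 5.
2. Count both reporting sentences from the same date, the last use of study product. For a completer the first window would then close, and the later rule open, at 6 + 4 = week 10, with no gap.
3. State what unexpectedness is judged against, and why that condition applies only in the first window.

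These are wording changes. They add no visit, measurement or analysis. The likely cost is one or two more SAE forms.
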